
#### 7.3. Randomisation

Participants will be randomised on a 1:1 basis to receive either TIVA or inhalational anaesthesia by a computer generated procedure. This computerised procedure will use a minimisation algorithm to ensure balance in treatment arm allocation across the following four stratification variables, factors thought to affect outcome either

through treatment effectiveness or underlying prognosis, also permitting appropriate exploratory subgroup analyses:

- 1) Surgical speciality (musculoskeletal/intra-abdominal/thoracic/vascular/other)
- 2) Expected duration of surgery (<2hours, ≥2hours)
- 3) Cancer surgery/non-cancer surgery
- 4) Preoperative frailty (Rockwood Frailty Score) Well/Vulnerable/Frail

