#### 10. Statistical considerations

A detailed statistical analysis plan will be drafted by the trial statistician, which will be finalised and approved by the CI and an independent statistician before the final data analysis. All statistical analyses will be undertaken on an intention to treat basis to preserve randomisation, avoid bias from exclusions and preserve statistical power. Hence all participants enrolled into the study, regardless of whether they received their randomised intervention, will be analysed according to their randomised group using data collected up to their 30-day time-point, or the last time-point prior to their withdrawal or loss to follow-up before this. Patients not receiving surgery or withdrawing consent for follow-up prior to surgery will not be included in relevant denominators.

For the primary outcome of blood glucose change from the start of surgery until the end of surgery, each randomised treatment arm's point estimates (and 95% confidence interval) will be reported. In addition, blood glucose measurements from the start of surgery until the end of surgery will be compared across randomised

treatment arms using independent samples t-tests, or Wilcoxon rank sum tests depending on the distribution of the data. The secondary clinical outcomes (incidence of myocardial injury and/or all-cause infection) will be assessed across trial arms using a chi-squared test. The continuous variables measuring mechanistic outcomes of glucose and metabolic profiles will initially be compared across trial arms using independent samples t-tests, or Wilcoxon rank sum tests (depending on the distribution of the data). Further comparisons across trial arms of blood glucose measures over time and the mechanistic outcomes over time will use repeated measures analyses, a statistically efficient approach that allows all of the follow-up data collated during the study to be used.

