For GlucoVITAL, four factors define sub-groups of interest: (1) Surgical speciality (intrabdominal/other); (2) Cancer surgery/non-cancer surgery; (3) Incidence of hyperglycaemia (glucose <7.8mmol/L) within first 24h of surgery (including at time of induction of anaesthesia); (4) Diabetes mellitus/no diabetes mellitus. Pre-specified sub-group analyses that will be undertaken using appropriate modelling techniques. These will be determined following examination of the distributions of the collected data. These exploratory sub-group analyses will have lower power than the main whole trial analysis but are hypothesis-generating and results will be scrutinised graphically via forest plots.

Descriptive statistics will be used to summarise the distribution of baseline variables across each of the randomisation arms. Continuous variables will be reported with means and 95% confidence intervals, if normally distributed, or medians and Interquartile Ranges (IQR) otherwise. Categorical variables will be reported using frequencies and percentages.

A Consolidated Standards of Reporting Trials (CONSORT) flow diagram will be produced, showing the frequency of participants:

- Assessed for eligibility
- Excluded prior to randomisation (and the frequency of each reason for exclusion)
- Allocated to each randomisation arm
- Receiving or not receiving their randomised treatment
- Followed-up at each protocol specified timepoints

 Lost to follow-up at each protocol specified timepoints (plus frequency of each reason for loss to follow-up)

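### The subgroup analyses are called pre-specified, but their method is to be settled after the collected data are examined, with no requirement that this look be blind to arm

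*Protocol*

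**What the plan says.** Section 10 states that "four factors define sub-groups of interest: (1) Surgical speciality (intrabdominal/other); (2) Cancer surgery/non-cancer surgery; (3) Incidence of hyperglycaemia" within 24 hours of surgery, and "4) Diabetes mellitus/no diabetes mellitus". It continues: "Pre-specified sub-group analyses that will be undertaken using appropriate modelling techniques". The next sentence reads: "These will be determined following examination of the distributions of the collected data". The results are described as lower in power than the whole-trial analysis, and they "are hypothesis-generating and results will be scrutinised graphically via forest plots". No treatment-by-factor contrast is mentioned.

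The same section promises a detailed SAP "which will be finalised and approved by the CI and an independent statistician before the final data analysis". Blinding is described only for the laboratory staff who measure fasting glucose and C-peptide (section 10.1) and for the steering committee's safety review (section 14.2).

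**The concern.** An analysis is pre-specified if its method is fixed before the data can influence it. Here the label and the following sentence do not agree. Whether the word *These* refers to the analyses or to the modelling techniques, something that determines the result is chosen after the data have been examined. The timing rule for the SAP does not close the gap. A SAP could comply with section 10 in full and still be completed after its approvers had seen glucose distributions by arm.

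The stated way of judging the results adds to this. A forest plot with no interaction estimate beside it invites the reader to compare strata by whether each interval crosses zero. That comparison often suggests that the treatment works in one stratum and not in the other when the true effect is the same in both. A publication could then cite the protocol's pre-specified label in support of such a finding.

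**Working it through.** **Inputs from the protocol.** Difference 0.6 mmol/L, SD 1.8 mmol/L, 5% two-sided, 90% power, 2% dropout, at least 390 patients (section 10.1); 450 recruited (sections 3 and 10.1); 1:1 allocation (section 7.3); four subgroup factors (section 10).

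**Assumptions.** The protocol gives no subgroup sizes, so the splits below are assumed. Normal approximations are used and the negligible wrong-direction tail is ignored. The number analysed is 450 × 0.98 = 441.

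**1. The plan's own figure.**
- n per arm = 2 × (1.960 + 1.282)² × 1.8² / 0.6² = 2 × 10.51 × 9 = 189.1, rounded up to 190, so 380 in total.
- With 2% dropout: 380 / 0.98 = 387.8, so 388.
- The protocol says at least 390. The figure reproduces.

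**2. Reading by within-stratum significance, true effect uniform at 0.6, 50/50 split.**
- Patients per stratum: 220.5.
- Standard error of the treatment difference in one stratum = 1.8 × √(4 / 220.5) = 0.242.
- Power per stratum = Φ(0.6 / 0.242 − 1.960) = Φ(0.515) = 0.697.
- Chance that exactly one stratum is significant = 2 × 0.697 × 0.303 = 0.42.

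**3. The same with an 80/20 split.**
- Power is 0.879 in the larger stratum and 0.347 in the smaller.
- Discordance = 0.879 × 0.653 + 0.121 × 0.347 = 0.574 + 0.042 = 0.62.

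**4. The same with no effect at all.**
- Discordance = 2 × 0.05 × 0.95 = 0.095 per factor.

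**5. Interaction test instead.**
- Under a uniform effect it is falsely positive in 5% of trials per factor.
- For at least one of four, taken as independent: 1 − 0.95⁴ = 0.185.

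**6. What an interaction test can detect.**
- Standard error at 50/50 = 1.8 × √(4 / 220.5 + 4 / 220.5) = 0.343.
- Power for an interaction as large as the whole planned effect = Φ(0.6 / 0.343 − 1.960) = Φ(−0.21) = 0.42.
- The same formula gives 0.36 at 70/30, 0.29 at 80/20 and 0.18 at 90/10.
- The interaction detectable with 90% power is 0.343 × 3.242 = 1.11 mmol/L at 50/50 and 1.39 mmol/L at 80/20.

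**The case against.** The strongest reply has three parts.

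- **The factors are fixed and the claims are modest.** The four factors are named in advance. On the natural reading only the modelling technique is left open, and the protocol itself calls the analyses exploratory and lower in power. This stands, and it limits the harm. It does not make a method chosen after examining the data pre-specified.
- **The detail belongs in the SAP, and the look may be harmless.** Model form and interaction tests are commonly left to a SAP. Examining distributions may mean a pooled check, like the one that decides between a t-test and a Wilcoxon test for the main comparison. This stands in part: the absence of an interaction test from the protocol would not be a finding by itself. But the protocol is not silent. It states a rule that lets data inform the choice, and it does not restrict the look to pooled data.
- **Forest plots are a normal display.** They show estimates with intervals and are compatible with an interaction test. This stands. The 42% is therefore conditional on a way of reading that the protocol neither states nor excludes.

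Two stronger readings are tempting. First, a reader might compound the discordance over four factors, reach more than 80%, and set that against 5%. The documents do not support this. It treats all four as independent baseline factors, whereas the hyperglycaemia factor uses glucose up to 24 hours from surgery and so includes values after randomisation. Nor is it like for like, because the interaction figure over four tests is about 19%.

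Second, a reader might infer that expected duration and frailty, which are minimised but not listed as subgroups, are known effect modifiers that have been dropped. Section 7.3 says only that the factors may act "through treatment effectiveness or underlying prognosis, also permitting appropriate exploratory subgroup analyses". That is permission, not a commitment, and it identifies neither factor as a modifier.

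**Conclusion.** The point holds as an inconsistency in section 10: the subgroup analyses carry a pre-specified label, while their method is to be settled after looking at the data, with no blinding condition and with visual inspection as the only stated criterion. It does not touch the primary comparison. Its consequence depends on how the plots are read. Under within-stratum reading, with a uniform 0.6 mmol/L effect, SD 1.8 and 441 analysed, strata would disagree in about 42% of trials for a 50/50 factor and about 62% for an 80/20 factor. The interaction test gives about 5% false positives per factor and about 19% over four. The splits are assumptions. The calculation applies to factors known before randomisation and not to the hyperglycaemia factor as defined. Because the analyses are declared exploratory, this is a correction worth making and not a threat to the trial's main conclusion.

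**What to change.** Replace the sentence that defers the choice with text such as:

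> For each subgroup factor measured before randomisation, a regression of glucose change on treatment, factor and their interaction is fitted. The interaction estimate and 95% CI are reported beside the forest plot, unadjusted for multiplicity and labelled exploratory. No claim rests on within-stratum significance.

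Add that this model is fixed in the SAP before anyone approving the SAP sees outcome data by arm. The regression has to be named because the main comparison is a t-test or Wilcoxon test, so there is no primary model to which an interaction could be added. The hyperglycaemia factor falls outside this wording as long as it includes glucose after randomisation; its handling should be stated separately.

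Adding expected duration and frailty is optional. With six factors the chance of at least one false positive rises to 1 − 0.95⁶, about 26% if independent.

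The cost is wording: no change to sample size, visits or data collection. Interaction tests will have low power (at most about 42% for an interaction of 0.6 mmol/L), so a null result must not be read as evidence of a uniform effect.

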fasting plasma glucose and C-peptide will be quantified by lab personnel blinded to clinical/glucose data. Based on previous work examining the effect of methylprednisolone on insulin resistance, 45 patients per arm are required to have a 90% chance of detecting (5% 2-sided significance) a difference of 1 SD (0.6) in HOMA-IR between intravenous and inhalational anaesthesia 24 hours after surgery (2% dropout).

3) Flow cytometry quantification of leukocytes, based on our previous data on glutamine dependence of T cells. Samples will be analysed before induction of anaesthesia, end of surgery and day one after surgery. Assuming 5% 2sided significance, SD of glutamine dependence of up to 7% and 90% power, 133 patients are required to detect a difference of 4% in glutamine dependence between modes of anaesthesia (allowing for nominal 2% dropout).

#### 11. Ethics

The CI must ensure that the study is conducted in accordance with the guidelines of the International Conference on Harmonisation, Good Clinical Practice (GCP) and UK legislation. All study documentation will be reviewed and approved by the research ethics committee prior to start of recruitment. Research Ethics Committee, Health Research Authority and Sponsor approvals will be in place before patient recruitment commences. The study will be sponsored by QMUL. Additionally, each participating site will ensure that the approval of the relevant trust Research & Development department and Ethics Committee is in place and a written confirmation is provided to the Sponsor.

# 11.1. Annual Safety Reporting

Not applicable.

#### 12. Public Involvement

The grant proposal for this study has been designed with the PPI members at The Patient, Carer & Public Involvement and Engagement (PCPIE) group (support (https://www.niaa-hsrc.org.uk/PCPIE). Furthermore, our PPI co-applicant have reviewed the protocol and will continue to advise us for the duration of the study including dissemination of the study results. Patient research partners will review the protocol and patient-facing documents to ensure that they are fit for purpose and

refine our consenting procedures. They will join our regular Trial Management Committee meetings and review participant recruitment progress.

# 13. Data Handling and Record Keeping

#### 13.1. Information governance

The study will be sponsored by Queen Mary University of London and will follow NHS and sponsor standard operating procedures for data storage and access and are consistent with the principles of the Data Protection Act and General Data Protection Regulation (GDPR).

# 13.2. Data management

Data will be transcribed onto the electronic CRF (eCRF) on the secure data entry web portal. Submitted data will be reviewed for completeness and consistency by authorised users within the trial coordinating team. Submitted data will be stored in Queen Mary University of London safe haven securely against unauthorised manipulation and accidental loss. Only authorised users at site, or at Barts Health NHS Trust will have access. Desktop security is maintained through usernames and passwords. Data back-up procedures are in place and a full audit trail will be kept. Storage and handling of confidential trial data and documents will be in accordance with the Data Protection Act 2018 (UK).

#### 13.3. Source Data

The eCRF will count as source data for patient reported outcomes collected during the 30-day follow-up. Patients' medical notes will act as source for the rest of the data. It is expected that the exact source data list will vary by site.

#### 13.4. Confidentiality

The PI has a responsibility to ensure that participant anonymity is protected and maintained. They must also ensure that their identities are protected from any unauthorised parties. The Sponsor will ensure that all participating partner organisations will maintain the confidentiality of all subject data and will not reproduce or disclose any information by which subjects could be identified, other than reporting of serious adverse events. In the case of special problems and/or competent authority queries, it is also necessary to have access to the complete trial records, provided that patient confidentiality is protected. Information with regards to study participants will be kept confidential and managed in accordance with the Data

Protection Act, NHS Caldicott Guardian, The Research Governance Framework for Health and Social Care and Research Ethics Committee Approval. The CI and the study team will adhere to these parameters to ensure that the participant's identity is protected at every stage of their participation within the study. Patients will be anonymised with regards to any publications relating to this study.

# 13.5. Record retention and archiving

During the course of research, the CI has full responsibility of all study records which must be kept in secure conditions at all times. The UK Policy Framework for Health and Social Care Research and Sponsor SOP, requires that research records are kept for 5 years after the study has completed. Archiving will be authorised by the Sponsor following submission of the end of study report. The Sponsor is responsible for maintaining and archiving the study TMF. The study database will be stored according to the Sponsor's policies. Electronic data sets will be stored indefinitely. The sites are responsible for maintaining and archiving all local records including the ISF and CRFs. These records should be archived together once authorisation has been given by the Sponsor. It is the responsibility of the PI to ensure a full set of records is collated and documented.

# 13.6. Monitoring and Auditing

The Sponsor or delegate retains the right to audit any study, study site or central facility. In addition, any part of the study may be audited by the funders where applicable. The GlucoVITAL study master documents may be audited by the Sponsor to ensure study activities are conducted according to the protocol, the Sponsor's standard operating procedures, GCP and the applicable regulatory requirements. In participating hospitals, local study documents may be selected for audit on a local basis. However, the GlucoVITAL study team will not routinely monitor data collection in individual hospitals or conduct source data verification.

# 14. Trial Management & Committees

#### 14.1. Trial management group

Day-to-day management will be co-ordinated by the Critical Care and Perioperative Medicine Research Group (CCPMG) based at Queen Mary University of London. The day-to-day conduct of the study trial will be led by the trial management group, under the management of the CI(s) or nominated deputy.

# 14.2. Trial steering committee (TSC)

The TSC will be periodically reviewing safety data, blind to the randomised arm, and liaising with the DMC regarding safety issues.

#### 14.3. Data Monitoring Committee (DMC)

The DMC, periodically reviewing safety data, split by randomised arm, to determine patterns and trends of events, identifying safety issues which would not be apparent on an individual case basis.

# 15. Finance and Funding

The GlucoVITAL study is funded by the Efficacy and Mechanism Evaluation (EME) Programme awarded to the CI. The funders will play no role in study design, conduct, data collection, data analysis, reporting or interpretation of the results.

# 16. Sponsorship and Insurance

The insurance that Queen Mary University of London has in place provides cover for the design and management of the study as well as "No Fault Compensation" for participants, which provides an indemnity to participants for negligent and nonnegligent harm.

# 17. Dissemination of Research Findings

Data arising from this research will be made available to the scientific community in a timely and responsible manner. A detailed scientific report will be submitted to a widely accessible scientific journal on behalf of the GlucoVITAL study group. At least one of the lay members will contribute to the dissemination of protocol and final manuscripts. Authorship of the final manuscript(s), interim publications, or abstracts will be decided according to active participation in the design, committee membership, accrual of eligible patients and statistical analysis. All authors will comply with internationally agreed requirements for authorship and will approve the final manuscript prior to submission. The funders, contributing centres (and participating investigators) will be acknowledged in the final manuscript. No investigator may present data from his/her centre separately from the rest of the study results unless approved by the study management team and the Sponsor. The full study report will be submitted to the funder and will also be made accessible via ISRCTN.

# 19. Appendices

#### 19.1. Appendix A

Definitions of infections Surgical site infection (superficial surgical site)

An infection at the surgical incision site which meets the following criteria:

- Involves only skin and sub-cutaneous tissue of the incision and
- The patient has at least one of the following:
  - purulent drainage from the superficial incision
  - organisms isolated from an aseptically obtained culture of fluid or tissue from the superficial incision
  - at least one of the following symptoms or signs of infection: pain or tenderness, localized swelling, redness, or heat, and superficial incision is deliberately opened by surgeon and is culture positive or not cultured. A culture-negative finding does not meet this criterion.
  - diagnosis of an incisional surgical site infection by a surgeon or attending physician

Surgical site infection (deep surgical site)

An infection at the surgical incision site which meets the following criteria:

- Involves deep soft tissues (e.g. fascial and muscle layers) of the incision and The patient has at least one of the following:
  - purulent drainage from the deep incision but not from the organ/space component of the surgical site
  - a deep incision spontaneously dehisces or is deliberately opened by a surgeon and is culture-positive or not cultured when the patient has at least one of the following symptoms or signs: fever (>38°C), or localized pain or tenderness. A culture-negative finding does not meet this criterion.
  - an abscess or other evidence of infection involving the deep incision is found on direct examination, during surgery, or by histopathologic or radiologic examination
  - diagnosis of an incisional surgical site infection by a surgeon or attending physician

Surgical site infection (organ/space)

An infection at the surgical incision site, excluding the fascia or muscle layers, which appears to be related to the surgical procedure and involves any part of the body, excluding the skin incision, fascia, or muscle layers, that is opened or manipulated during the operative procedure and the patient has at least one of the following:

• purulent drainage from a drain that is placed through a stab wound into the organ/space

- organisms isolated from an aseptically obtained culture of fluid or tissue in the organ/space
- an abscess or other evidence of infection involving the organ/space that is found on direct examination, during reoperation, or by histopathologic or radiologic examination
- diagnosis of an organ/space surgical site infection by a surgeon or attending physician

#### Pneumonia

This is defined as two or more serial chest radiographs with at least one of the following (one radiograph is sufficient for patients with no underlying pulmonary or cardiac disease):

- a) new or progressive and persistent infiltrates
- b) consolidation
- c) cavitation

